Appendix Table 1. Protocol Specified Contraceptive Methods

Single Methods	Combination Methods

Intrauterine Devices (IUDs)
 
 • Copper T 380A IUD • LNG 20 IUD 
Tubal Sterilization
	
Estrogen and Progesterone plus Barrier
 
 • Combined oral contraceptives plus condom* • Transdermal patch plus condom* • Vaginal ring plus condom* • Implant plus condom* • Injection plus condom* 
Partner’s vasectomy must be used with a hormonal method.

* (without spermicide and excluding lambskin)

The investigator will counsel all subjects on the most effective method(s) for avoiding pregnancy during the study.

4) Additional Requirements for Male Subjects and Recommendations for Partners of Female Subjects

Male subjects must agree to use condoms (without spermicide and excluding lambskin) during heterosexual intercourse and avoid sperm donation while enrolled in the study and for at least 90 days after administration of the last dose of study drug. Partners of female subjects should be encouraged to use condoms during heterosexual intercourse while enrolled in the study.

Use of condoms, with or without spermicide, has been proven to decrease the risk of transmission of HIV and other sexually transmitted diseases. The use of spermicide is not recommended if the subject or subject’s partner is infected with HIV.

5) Procedures to be Followed in the Event of Pregnancy

Subjects will be instructed to notify the investigator if they become pregnant at any time during the study, or if they become pregnant within 30 days or 4 weeks of last study drug dose. Subjects who become pregnant or who suspect that they are pregnant during the study must report the information to the investigator and discontinue study drug immediately. Subjects whose partner has become pregnant or suspects she is pregnant during the study must report the information to the investigator. Instructions for reporting pregnancy, partner pregnancy, and pregnancy outcome are outlined in Section [7.7.2.1](#).

Appendix 6. Definitions of Stage 3 Opportunistic Illnesses in HIV (CDC Guidelines)

- Candidiasis of bronchi, trachea, or lungs
- Candidiasis of esophagus
- Cervical cancer, invasive
- Coccidioidomycosis, disseminated or extrapulmonary
- Cryptococcosis, extrapulmonary
- Cryptosporidiosis, chronic intestinal (> 1 month duration)
- Cytomegalovirus disease (other than liver, spleen or nodes)
- Cytomegalovirus retinitis (with loss of vision)
- Encephalopathy, HIV-related
- Herpes simplex: chronic ulcer(s) (> 1 month duration); or bronchitis, pneumonitis or esophagitis
- Histoplasmosis, disseminated or extrapulmonary
- Isosporiasis, chronic intestinal (> 1 month duration)
- Kaposi's sarcoma
- Lymphoma, Burkitt's (or equivalent term)
- Lymphoma, immunoblastic (or equivalent term)
- Lymphoma, primary, of brain
- *Mycobacterium avium* complex or *Mycobacterium kansasii*, disseminated or extrapulmonary
- *Mycobacterium tuberculosis*, of any site, pulmonary, disseminated or extrapulmonary
- *Mycobacterium*, other species or unidentified species, disseminated or extrapulmonary
- *Pneumocystis jirovecii* (previously known as "*Pneumocystis carinii*") pneumonia
- Pneumonia, recurrent
- Progressive multifocal leukoencephalopathy
- *Salmonella* septicemia, recurrent
- Toxoplasmosis of brain
- Wasting syndrome attributed to HIV infection

CDC Stage-3-Defining Opportunistic Illnesses in HIV Infection - 2014 {[Schneider 2008](#)}

## LIST OF ABBREVIATIONS

AE	adverse event
ALT	alanine aminotransferase
ANOVA	analysis of variance
ART	antiretroviral therapy
ARV	antiretroviral
AST	aspartate aminotransferase
BL	baseline
BLQ	below the limit of quantification
BMI	body mass index
CAVR/CAVD	cell-associated HIV-1 RNA/DNA
CRF	case report form
CSR	clinical study report
DLTs	dose-limiting toxicities
DMC	data monitoring committee
ECG	electrocardiogram
ESDD	early study drug discontinuation
eCRF	electronic case report form
FU	follow-up
GLSM	geometric least-squares means
GSI	Gilead Sciences, Inc
HLT	high level term
HLGT	high level group term
ICS	intracellular cytokine staining
ISGs	interferon-stimulated genes
IVRS	interactive voice response system
IWRS	interactive web response system
LLOQ	lower limit of quantitation
LLT	lower level term
LOQ	limit of quantitation
MAD	multiple ascending dose
MedDRA	medical dictionary for regulatory activities
PBMC	peripheral blood mononuclear cell
PT	preferred term
PVE	Pharmacovigilance and Epidemiology
Q1	first quartile

Q3	third quartile
SAE	serious adverse event
SAP	statistical analysis plan
SCA	single copy assay
SD	standard deviation
SEC	safety evaluation committee
SOC	system organ class
TEAE	treatment-emergent adverse event
TFLs	tables, figures, and listings
ULN	Upper limit of normal
ULOQ	upper limit of quantification
VES (GS-9620)	Vesatolimod
WHO	World Health Organization

## PHARMACOKINETIC ABBREVIATIONS

$AUC_{last}$	area under the concentration versus time curve from time zero to the last quantifiable concentration
$AUC_{inf}$	area under the concentration versus time curve extrapolated to infinite time, calculated as $AUC_{0-last} + (C_{last}/\lambda_z)$
$\%AUC_{exp}$	Percentage of AUC extrapolated between $AUC_{0-last}$ and $AUC_{inf}$
$C_{last}$	last observed quantifiable concentration of the drug in plasma
$C_{max}$	maximum observed concentration of drug in plasma
$CL/F$	apparent oral clearance after administration of the drug: at single dose: $CL/F = Dose/AUC_{inf}$ , where “Dose” is the dose of the drug at steady state: $CL/F = Dose/AUC_{tau}$ , where “Dose” is the dose of the drug
$T_{1/2}$	estimate of the terminal elimination half-life of the drug in plasma, calculated by dividing the natural log of 2 by the terminal elimination rate constant ( $\lambda_z$ )
$T_{last}$	time (observed time point) of $C_{last}$
$T_{max}$	time (observed time point) of $C_{max}$
$V_z/F$	apparent volume of distribution of the drug
$\lambda_z$	terminal elimination rate constant, estimated by linear regression of the terminal elimination phase of the concentration of drug versus time curve

## 1. INTRODUCTION

This statistical analysis plan (SAP) describes the statistical analysis methods and data presentations to be used in tables, figures, and listings (TFLs) in the clinical study report (CSR) for Study GS-US-382-1450. This SAP is based on the study protocol Amendment 7 dated 16 January 2019 and the electronic case report form (eCRF). The SAP will be finalized before database finalization for the final analysis. Any changes made after the finalization of the SAP will be documented in the CSR.

### 1.1. Study Objectives

The primary objectives of this study are as follows:

- To evaluate the safety and tolerability of escalating, multiple doses of Vesatolimod (VES [GS-9620]) in HIV-1 infected virologically suppressed adults on antiretroviral therapy (ART)
- To evaluate the virologic effect of VES as measured by changes in plasma HIV-1 RNA

The secondary objectives of this study are as follows:

- To evaluate the plasma pharmacokinetics (PK) of VES
- To evaluate the pharmacodynamics (PD) of VES as measured by changes in interferon-stimulated genes (ISGs) and serum cytokines in whole blood compared to placebo
- To evaluate effects of VES on whole blood immune cell activation (CD4 and CD8 T cell, NK cell)

The exploratory objectives of this study are as follows:

- [REDACTED]
- [REDACTED]
- [REDACTED]

## 1.2. Study Design

This is a phase 1b, randomized, double-blinded, placebo-controlled, multi-cohort dose-escalation study with dose cohorts: Cohort 1 (1 mg Dose), Cohort 2 (2 mg Dose), Cohort 3 (4 mg Dose), Cohort 4 (6 mg Dose), Cohort 5 (8 mg Dose), Cohort 6 (three administrations of 10 mg Dose, followed by seven administrations of 12 mg Dose; Safety Evaluation Committee [SEC] review of the 10mg safety data will be required prior to dose escalating to 12mg), and optional Cohort 7

CCI

Two additional optional adaptive cohorts, Cohort 8

CCI

and Cohort 9

CCI

HIV-1 infected male and non-pregnant, non-lactating female adults who have been virologically suppressed (HIV-1 RNA < 50 copies/mL) on ART for  $\geq 12$  consecutive months prior to screening may be eligible for entry (refer to the protocol for complete inclusion and exclusion criteria). Eligible subjects are randomly assigned to 1 of the following 2 treatment groups in a 6:2 ratio for each cohort. CCI

- Cohort 1 (n = 8): Blinded VES 1 mg (n = 6) vs. Placebo (n = 2)
- Cohort 2 (n = 8): Blinded VES 2 mg (n = 6) vs. Placebo (n = 2)
- Cohort 3 (n = 8): Blinded VES 4 mg (n = 6) vs. Placebo (n = 2)
- Cohort 4 (n = 8): Blinded VES 6 mg (n = 6) vs. Placebo (n = 2)
- Cohort 5 (n = 8): Blinded VES 8 mg (n = 6) vs. Placebo (n = 2)
- Cohort 6 (n = 8): Blinded VES 10/12 mg (n = 6) vs. Placebo (n = 2)

Central randomization is used. Enrollment will initially be opened for Cohort 1 only. The SEC will review study progress, safety and virology results of enrolled subjects. After all subjects in a cohort have received at least three doses (Cohorts 1 to 3, and 6) or five doses (Cohorts 4 and 5), the SEC will review safety data from that cohort, including adverse events (AEs) and clinical laboratory results (including plasma HIV-1 RNA) before approving the next dose escalation. CCI

A cohort may be suspended if  $\geq 2$  out of 6 subjects receiving VES experience one or more dose-limiting toxicities (DLTs) considered related to study drug. Subjects will receive a total of either 6 doses in Cohorts 1 to 3, 10 doses in Cohorts 4

to 6, CCI of their assigned study treatment administered once every other week. For all subjects in Cohort 6, Dose 4 (Day 43) will occur after SEC review has been completed. If dose escalation is approved by the SEC, subjects in Cohort 6 will receive 12 mg of VES or placebo from Doses 4 to 10; if dose escalation is not approved by the SEC, subjects will continue receiving 10 mg of VES or placebo from Doses 4 to 10.

For Cohorts 1 to 3, dosing visits will occur at Day 1, Day 15, Day 29, Day 43, Day 57, and Day 71. For Cohorts 4 to 9, dosing visits will occur at Day 1, Day 15, Day 29, Day 43, Day 57, Day 71, Day 85, Day 99, Day 113 and Day 127. CCI

For Cohorts 1 to 4, subjects will fast for at least 2 hours before dosing. For Cohorts 5 to 8, subjects will fast overnight (at least 8 hours) before dosing. CCI

The Investigator will verify the subject's continued eligibility for dosing at post-Baseline dosing visits, including the absence of DLTs and (for females of childbearing potential) a negative urine pregnancy test, prior to dosing. All doses will be directly administered by blinded site staff.

Laboratory analyses (hematology, serum chemistry, and urinalysis) will be performed weekly for Cohorts 1 to 3. For Cohorts 4 to 9, these labs will be collected on dosing days, seven days post dose (starting from Dose 4), at end of study, and early study drug discontinuation (ESDD). For Cohorts 6, CCI these labs will also be collected on Day 2 and two days post dose (starting from Dose 5). CCI

Urine pregnancy test (for females of childbearing potential) will be performed prior to each dose. Vital signs (blood pressure, pulse, respiration rate and temperature) will be measured at all dosing visits.

Plasma HIV-1 RNA will be measured at every visit except Pre-Baseline (Day -13). Cell-associated HIV-1 RNA/DNA (CAVR/CAVD), and plasma HIV-1 RNA by SCA will be collected immediately before and two days post Doses 1, 4, 6 and at end of the study (Cohort 1 to 3); immediately before and two days post Doses 1, 5, 10 and at end of the study (Cohorts 4 to 9). CCI

Peripheral blood immune cell numbers for T/B/NK/pDC/mDC including: CD4 and CD8 populations, CD4/CD8 ratio, CD4% and lymphocyte activation (T, B and NK cells) by flow cytometry will be collected immediately before and two days post Doses 1, 3, and 6 (Cohorts 1 to 3), and immediately before and two days post Doses 1, 5, 10 and at end of the study (Cohorts 4 to 9). FoxP3+ Treg cells by flow cytometry will be collected immediately before Doses 1, 3, and 6 (Cohorts 1 to 3), and immediately before Doses 1, 5 and 10 (Cohort 4 to 9). CCI

Changes in the levels of antiviral cytokines and inflammatory markers by chemiluminescence will be collected immediately before and 2 days and 7 days after each dose, and at the end of the study (Cohorts 1 to 3). For subjects in Cohorts 4 to 9, they will be collected immediately before, post dose days 1, 2 and 7 after Doses 1, 4 (only if Cohort 6 subjects receive 12 mg at Dose 4), 5 and 10. CCI

PBMC intracellular cytokine staining (ICS) for Treg cells will be done immediately before and 2 days after Doses 1 and 6 for subjects in Cohorts 1 to 3. HIV-specific T-cell responses by ELISPOT will be collected at Pre-Baseline/Day -13, immediately before Dose 6 and at the end of study for subjects in **Cohorts 1 to 3**. For subjects in Cohorts 4 to 9, HIV-specific polyfunctional T cell ICS and HIV-specific T-cell responses by ELISPOT will be collected at Pre-Baseline/Day -13 and at the end of the study. CCI

Whole blood ISG mRNA panel will be performed immediately before and 2 days and 7 days after each dose of study drug and at the end of the study (Day 101) (for Cohorts 1 to 3) and immediately before and 1, 2 and 7 days after Doses 1, 4 (only if Cohort 6 subjects receive 12 mg starting at Dose 4), 5 and 10. CCI

Assessments of adverse events, concomitant medications and symptom-directed physical examination are performed at each visit.

Blood samples will be collected to determine plasma VES concentrations and plasma ARV concentrations at the following time points relative to study drug dosing:

**Plasma VES concentrations** at the following time points **for all cohorts**:

- Pre-dose ( $\leq 5$  minutes prior to dosing), 0.5, 1, 2, 4, 6, 8, 10, and 12 hours post dose at Day 1; then one sample 48 hours post dose at Day 3
- **If the SEC approves the dose escalation to 12 mg in Cohort 6, starting from Dose 4 and onwards**, plasma VES concentrations will also be collected on Day 43 (Dose 4): Pre-dose ( $\leq 5$  minutes prior to dosing), 0.5, 1, 2, 4, 6, 8, 10, and 12 hours post dose; then one sample 48 hours post dose at Day 45.

**Plasma ARV concentrations**: a single trough ARV PK sample will be collected at Pre-Baseline/Day -13 (**Cohorts 1 to 3**) or at Screening, Day 29, Day 57, Day 85 and Day 99 (**Cohort 5**), or at Screening, Day 57 and Day 99 (**Cohorts 6** CCI CCI

### 1.3. Sample Size and Power

No power calculation was performed because this is an exploratory study to characterize the safety and efficacy of VES in HIV-1 infected patients.

## **2. TYPE OF PLANNED ANALYSIS**

### **2.1. Interim Analyses**

#### **2.1.1. Interim Blinded Analyses**

SEC will review the progress of the study and perform interim reviews of the safety data in order to protect subject welfare and preserve study integrity. To ensure the best interests of the participants, the SEC will recommend to the sponsor if the nature, frequency, and severity of adverse effects associated with the study treatment warrant the early termination of the study, the continuation of the study, or the continuation of the study with modifications.

The initial meeting of the SEC has occurred prior to the first dose of Cohort 1. This meeting formally established the SEC and thoroughly acquainted the SEC with the protocol and the SEC Charter. Subsequent SEC analyses have been performed after all subjects enrolled in each Cohort received at least three doses (Cohorts 1 to 3, and 6) or five doses (Cohorts 4 to 5) to review the safety and virology data before approving the opening of enrollment in the next Cohort or dose escalation within the same Cohort (Cohort 6).

The SEC's role and responsibilities and the scope of analysis to be provided to the SEC are provided in a mutually agreed upon charter, which defines the SEC membership, meeting logistics, and meeting frequency.

#### **2.1.2. Interim Unblinded Analyses**

Prior to the final analysis, selected individuals from Gilead were unblinded to assess the interim safety, virology, biomarker, and PK data of VES. This group may consist of at least one representative from Clinical Research, Biostatistics, Clinical Pharmacology, Pharmacovigilance/Epidemiology, Biomarkers, Clinical Virology and may include other personnel as necessary.

The access to individual unblinded data (safety, virology, biomarker and PK) was limited only to data relevant for analysis by the function representatives and was summarized at the group level for regulatory documents and external submissions without revealing individual subject identification to protect study blind at the subject level. This group reviewed data (safety, virology, biomarker and PK) to support development of new clinical protocols, regulatory documents, and conference submissions.

### **2.2. Final Analysis**

After all subjects have completed the study, outstanding data queries have been resolved or adjudicated as unresolvable, and the data have been cleaned and finalized, the study blind will be broken and the final analysis of the data will be performed.

### **3. GENERAL CONSIDERATIONS FOR DATA ANALYSES**

Analysis results will be presented using descriptive statistics. For categorical variables, the number and percentage of subjects in each category will be presented; for continuous variables, the number of subjects (n), mean, standard deviation (SD) or standard error (SE), median, first quartile (Q1), third quartile (Q3), minimum, and maximum will be presented.

All statistical tests will be 2-sided and performed at the 5% significance level unless otherwise specified.

By-subject listings will be presented for all subjects in the All Randomized Analysis Set and sorted by subject ID number, visit date, and time (if applicable), unless specified otherwise. Data collected on log forms, such as AEs, will be presented in chronological order within the subject. The treatment group to which subjects were randomized will be used in the listings. Age, sex at birth, race, and ethnicity will be included in the listings, as space permits.

#### **3.1. Analysis Sets**

Analysis sets define the subjects to be included in an analysis. Analysis sets and their definitions are provided in this section. Subjects included in each analysis set will be determined before the study blind is broken for analysis. The analysis set will be identified and included as a subtitle of each table, figure, and listing. A summary of the number and percentage of subjects in each analysis set will be provided by treatment group and in total for all cohorts combined.

##### **3.1.1. All Randomized Analysis Set**

The All Randomized Analysis Set includes all subjects who were randomized into the study. This is the primary analysis set for by-subject listings.

##### **3.1.2. Full Analysis set**

The Full Analysis Set (FAS) will include all subjects who (1) were randomized into the study and (2) have received at least one dose of study drug. Subjects will be grouped according to the treatment to which they were randomized. For the FAS, all efficacy data, including data collected after the last dose of study drug, will be included, unless specified otherwise. This is the primary analysis set for efficacy analyses.

##### **3.1.3. Safety Analysis Set**

The Safety Analysis Set will include all subjects who (1) were randomized into the study and (2) have received at least 1 dose of study drug. All the data collected up to 30 days after permanent discontinuation of the study drug will be included in the safety summaries, unless specified otherwise. Subjects will be grouped according to the treatment they actually received. This is the primary analysis set for safety analyses.

### **3.1.4. VES Pharmacokinetic Analysis Set**

The VES PK Analysis Set will include all subjects who (1) were randomized into the study, (2) have received at least 1 dose of active VES, and (3) have at least 1 nonmissing steady state PK parameter for VES. This is the primary analysis set for detailed PK analysis of intensive PK sampling.

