8.2.1.4. Pharmacokinetics

8.2.1.4.1 GS-9620 Pharmacokinetic Analysis Set

The GS-9620 pharmacokinetic (PK) analysis set will include all subjects who are randomized and have received at least one dose of study drug and for whom PK parameters of analyte GS-9620 are available.

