## 8. PHARMACOKINETIC ANALYSES

### 8.1. PK Sample Collection

Plasma VES (concentrations will be collected at the following time points **for all cohorts** relative to the Dose 1 on Day 1:

- Pre-dose ( $\leq 5$  minutes prior to dosing), 0.5, 1, 2, 4, 6, 8, 10, and 12 hours post-dose at Day 1; then one sample 48 hours post dose at Day 3

Plasma VES concentrations will be collected at the following time points **for Cohort 6** relative to the Dose 4 on Day 43:

- Pre-dose ( $\leq 5$  minutes prior to dosing), 0.5, 1, 2, 4, 6, 8, 10, and 12 hours post dose at Day 43; then one sample 48 hours post-dose at Day 45.

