**Table 8-1. PK Parameters for VES**

Analyte	Parameters
VES (Single Dose)	$C_{max}$ , $T_{max}$ , $C_{last}$ , $T_{last}$ , $AUC_{last}$ , $AUC_{inf}$ , $\%AUC_{exp}$ , $T_{1/2}$ , $Vz/F$ , $CL/F$ , and $\lambda_z$

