#### 8.3.2. Dose Proportionality

If data are available, dose proportionality will be obtained by comparing PK parameters of VES across all dose levels for Cohorts 1-6.

Dose proportionality will be evaluated based on the power model and the ANOVA method.

The following PK parameters and dose levels will be included in both the power model and ANOVA method:

	Day	Doses (mg)	PK Parameters
VES (single dose)	1	1, 2, 4, 6, 8, 10, 12	$AUC_{last}$ , $AUC_{inf}$ , $C_{max}$

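### The SAP's PK analysis set requires a steady-state parameter that the trial never derives, so at least 30 of the 36 active subjects are excluded

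*SAP*

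**What the plan says.** SAP 3.1.4 sets three conditions for the VES PK Analysis Set: the subject was randomized, received at least one dose of active VES, and must "have at least 1 nonmissing steady state PK parameter for VES". It names this the primary set for the detailed analysis of the intensive PK sampling.

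SAP 8.1 describes the sampling. In all cohorts the profile is taken "relative to the Dose 1 on Day 1", running to 12 hours, "then one sample 48 hours post dose at Day 3". Only Cohort 6 has a second profile, "relative to the Dose 4 on Day 43". SAP 1.2 makes that second profile conditional on the Safety Evaluation Committee approving escalation to 12 mg.

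The only row of Table 8-1 opens with the label "VES (Single Dose". The input table for dose proportionality in SAP 8.3.2 carries the same label and is assigned to Day 1. The list of parameters to be calculated in SAP Appendix 1 has no AUCtau, Ctau or steady-state clearance.

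Protocol 8.2.1.4.1 defines the corresponding set as randomized, dosed subjects "for whom PK parameters of analyte GS-9620 are available", without mentioning steady state.

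**The concern.** An analysis set should be defined by data the trial will produce. Here the entry condition is a kind of parameter that the sampling schedule and the parameter list do not provide. SAP 8.2 determines the PK parameters in subjects in this set, and SAP 8.3.1 confines the listings and summaries of concentrations and parameters to it. Plasma PK is the first secondary objective. If the rule is programmed as written, that objective has no evaluable subject in Cohorts 1 to 5. If the programmer instead applies the rule that was probably meant, the analysis departs from the SAP without a record. SAP 3.1 also requires membership of each set to be settled before the blind is broken, so the rule has to be usable as it stands.

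**Working it through.** The documents give no size for the PK set, so there is no stated figure to reproduce. The set was counted from the SAP's own rules.

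**Inputs**

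- Active subjects: 6 per cohort, Cohorts 1 to 6 (SAP 1.2 and 3.2), so 6 × 6 = 36.
- Profiles: Dose 1 in every cohort; Dose 4 in Cohort 6 only (SAP 8.1).
- Parameters: single dose only (SAP Table 8-1, 8.3.2, Appendix 1).
- Dosing interval: 14 days × 24 h = 336 h (Protocol 1.4).
- Terminal half-life: medians of 17.16 to 26.96 h in healthy subjects at 1, 2 and 4 mg (Protocol 1.2.3.1); about 8 to 25 h in HBV or HCV infection (Protocol 1.4).
- Dose-proportionality reference: 1 mg, with six contrasts against it (SAP 8.3.2, ANOVA).

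**Step 1. Count the set under each reading**

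| Reading of the third condition | In the set | Excluded | 1 mg group |
|---|---|---|---|
| Literal: no planned parameter is a steady-state one | 0 | 36 (100%) | empty |
| Generous: Cohort 6 Day 43 counts as steady state | at most 6 | at least 30 (30/36 = 83%) | empty |
| Protocol 8.2.1.4.1: any available parameter | up to 36 | 0 | up to 6 |

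**Step 2. Consequence for dose proportionality**

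All six ANOVA contrasts compare a dose with 1 mg. With no 1 mg subject in the set, none can be estimated. Under the generous reading, the power model would have only the 10 mg and 12 mg profiles of the same six subjects. That is a dose range of 12/10 = 1.2-fold instead of 12/1 = 12-fold.

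**Step 3. Could the Day 43 profile be steady state?**

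It follows the first 12 mg dose, after three doses of 10 mg. With one-compartment decay at the terminal half-life, the fraction left after one interval is f = 2^(−336/t½), and the accumulation ratio is R = 1/(1 − f).

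| t½ (h) | Half-lives in 336 h | f | R |
|---|---|---|---|
| 8 | 42.0 | 2.3 × 10⁻¹³ | 1.0000 |
| 17.16 | 19.6 | 1.3 × 10⁻⁶ | 1.0000 |
| 25 | 13.4 | 9.0 × 10⁻⁵ | 1.0001 |
| 26.96 | 12.5 | 1.8 × 10⁻⁴ | 1.0002 |

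At the longest quoted half-life about 0.02% of a dose remains when the next is given. Day 43 is in effect another single-dose profile, and the SAP itself places 12 mg under its single-dose label.

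**Step 4. Look for steady-state terms elsewhere**

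They appear in the two-part definition of CL/F, where the steady-state form needs AUCtau, and in the decimal-place list in SAP Appendix 3. AUCtau is not among the parameters to be calculated, and no planned analysis uses either mention.

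**The case against.** The best defence is that the SAP contradicts itself rather than consistently prescribing an empty set. SAP 8.2.2 says parameters will be generated for every subject in whom they can be derived. SAP 8.3.2 compares all dose levels across Cohorts 1 to 6 and names no analysis set. Together with Table 8-1 and the protocol definition, these show what was intended. An empty set would be obvious at the first programming run, so it could hardly bias a result unnoticed. The study is exploratory, and PK is a secondary objective.

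Much of this is fair. The phrase looks like a drafting carry-over, the restriction on dose proportionality is inherited through SAP 8.2 rather than restated in 8.3.2, and the primary safety and virology endpoints are untouched. It does not rescue the definition, however. Generating parameters for everyone under 8.2.2 does not lift the limit in 8.3.1 on what is listed and summarized. SAP 3.1.4 also claims the intensive PK analysis for this set. A rule that can be read as giving 0, 6 or 36 subjects still needs correcting.

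The half-lives come from other populations and, at most, 4 mg, whereas this trial goes up to 12 mg. That extrapolation bears only on the six Cohort 6 subjects. Cohorts 1 to 5 have no profile after Dose 1, whatever the kinetics.

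**Conclusion.** The concern holds. As written, SAP 3.1.4 admits 0 of 36 active subjects, or at most 6 on the most generous reading. At least 83% are excluded, including the whole 1 mg reference group. The counts assume six treated active subjects with usable profiles in each of Cohorts 1 to 6 and, for the figure of 6, that the 12 mg escalation and its sampling took place. The conclusion rests on the sampling schedule and the parameter labels; the negligible carry-over is supporting evidence only. The PK data and sampling are not deficient. The fault is confined to the definition of the set, but that definition governs the whole analysis of a secondary objective and should be corrected before set membership is fixed.

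**What to change.** In SAP 3.1.4, delete the words *steady state* from the third condition, so that any nonmissing VES PK parameter qualifies. This agrees with Protocol 8.2.1.4.1 and admits up to 36 subjects. Specifying a single-dose parameter from Day 1, or from Day 43 in Cohort 6, would also work. Plain deletion is slightly cleaner because it avoids putting a label on a profile taken at the fourth dose.

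In the same edit, correct the dose-proportionality table in SAP 8.3.2, which lists 12 mg under Day 1 although 12 mg is first given on Day 43.

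The cost is one phrase and one table entry, with no new data or sampling. If the SAP is already final, its Section 1 requires the change to be documented in the clinical study report.
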